## **5.2. Participant Disposition**

The number of participants screened for the study will be provided.

Summary of study disposition post randomization will be provided by study intervention group as randomized for the following:

- Number of participants randomized; this frequency count will be used as the denominator to calculate the percentages described below
- Number and percentage of participants treated
- Number and percentage of participants who completed the study
- Number and percentage of participants who discontinued the study
- Reasons for discontinuation from the study

## **5.3. Primary Endpoint(s) Analysis**

### **5.3.1. Definition of Endpoint(s)**

The primary efficacy parameter will be the proportion of participants gaining 3 lines or more from baseline in mesopic, high contrast, binocular DCNVA without losing more than 5-letters of mesopic, high contrast, binocular CDVA with the same refractive correction at Day 30, Hour 3.

### **5.3.2. Main Analytical Approach**

The primary efficacy parameter will be analyzed using a chi-square test with 2-sided 95% confidence interval based on the normal approximation based on pooled variance without continuity correction.

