6.3. Measures to Minimize Bias: Randomization and Blinding

All participants will be centrally assigned to randomized study intervention using the IxRS. Randomization and kit assignment will be conducted on Day 1 (baseline). At Day 1, participants will be randomized in a 1:1 ratio into 1 of the 2 study groups. This randomization will be stratified by age (2 groups: ≤ 50 years and > 50 years), baseline binocular DCNVA (2 groups: 20/40 to 20/60 inclusively, and worse than 20/60), iris color (brown and non-brown), and emmetropes/non-emmetropes. A maximum of 50% (100 per arm) of the participants enrolled will have brown iris color, and a maximum of 25% (50 per arm) of the participants will be non-emmetropes (a sphere outside of -0.50 D to +0.75 D and/or a cylinder greater than 0.75 D).

AGN-190584

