9.4.1.2. Primary Analyses

The proportion of participants gaining 3 lines or more in mesopic, high contrast, binocular DCNVA at Day 30, Hour 3 will be analyzed using chi-square test. Missing data will be regarded as 3-line gain failure.

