## 1.1. Study Design

Study 1883-302-013 is a multicenter, double-masked, randomized, vehicle-controlled, parallel group, phase 3 study evaluating the efficacy and safety of AGN-190584 (1.25% pilocarpine) dosed once daily, bilaterally, over a period of 30 days in participants with presbyopia. The study population will consist of adult male and female participants with objective and subjective evidence of presbyopia. Approximately 200 participants per group will be randomized.

Participants will be randomized in a 1:1 ratio to receive either AGN-190584 or vehicle dosed once daily, in each eye, for 30 days. This randomization will be stratified by age (2 groups:  $\leq 50$  years and  $> 50$  years), baseline binocular DCNVA (2 groups: 20/40 to 20/60 inclusively, and worse than 20/60), iris color (brown and non-brown), and emmetropes/non-emmetropes. This study consists of the following visits: screening (Days -30 to -1), Day 1 (baseline), and Days 3, 7, 14, and 30.

Study interventions, either AGN-190584 or vehicle will be administered as topical eye drop once daily. Following the study schema (Figure 1-1), study intervention will be administered by designated site personnel on visit days and at home by the participant in-between office visits, ideally prior to starting their day. On the day before office visits, the study intervention must be administered no less than 16 hours before the scheduled visit time.

[figure not shown]

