## **2. Statistical Hypotheses**

For the primary efficacy analysis, the null hypothesis is that there is no difference between AGN-190584 ophthalmic solution and vehicle dosed bilaterally, once daily for 30 days in the proportion of participants gaining 3 lines or more from baseline in mesopic, high contrast, binocular DCNVA without losing more than 5-letters of mesopic, high contrast, binocular CDVA with the same refractive correction at Day 30, Hour 3. The alternative hypothesis is that there is a difference between AGN-190584 ophthalmic solution and vehicle.

For the key secondary efficacy analysis, the null hypothesis is that there is no difference between AGN-190584 ophthalmic solution and vehicle dosed bilaterally, once daily for 30 days in the proportion of participants gaining 3 lines or more from baseline in mesopic, high contrast, binocular DCNVA at Day 30, Hour 6. The alternative hypothesis is that there is a difference between AGN-190584 ophthalmic solution and vehicle.

The hypotheses will be tested using chi-square tests at a significance level of 5%.

AGN-190584

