## **5.4. Secondary Endpoint(s) Analysis**

### **5.4.1. Key Secondary Analysis**

The key secondary efficacy endpoint will be the proportion of participants gaining 3 lines or more from baseline in mesopic, high contrast, binocular DCNVA at Day 30, Hour 6. The key secondary efficacy parameter will be analyzed in the same way as the primary efficacy parameter.

AGN-190584

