**5.4.2. Other Secondary Analyses**

Other secondary efficacy endpoints include:

1. Proportion of participants gaining 3-lines or more in mesopic, high contrast, binocular, DCNVA at Day 30, Hour 8.
2. Change from baseline in mesopic, high contrast, binocular DCNVA letters at Day 30, Hour 0.5.
3. Proportion of participants achieving 20/40 or better in photopic, high contrast, binocular, DCNVA at Day 30, Hour 1.
4. Change from baseline in Mesopic NVPTQ Performance score at Day 30, Hour 3.
5. Change from baseline in photopic, high contrast, binocular DCIVA letters at Day 30, Hour 3.
6. Proportion of participants gaining 3-lines or more in mesopic, high contrast, binocular, DCNVA at Day 30, Hour 10.
7. Change from baseline in mesopic, high contrast, binocular DCNVA letters at Day 30, Hour 0.25.
8. Proportion of participants achieving 20/40 or better in photopic, high contrast, binocular, DCNVA at Day 30, Hour 3.
9. Change from baseline in Mesopic NVPTQ Satisfaction score at Day 30, Hour 3.
10. Change from baseline in PICQ Coping score at Day 30, Hour 3.
11. Change from baseline in PICQ Impact score at Day 30, Hour 3.

All secondary endpoints related to proportion of participant gaining 3 lines or more or achieving 20/40 better (endpoints 1, 3, 6 and 8) will be analyzed with the same analysis method as the primary efficacy parameter.

Timepoints are defined as scheduled measurement times made for each visit. Change from baseline in mesopic, high contrast, binocular DCNVA letters (endpoints 2 and 7) will be analyzed using mixed-effects model with repeated measures (MMRM) by timepoint that includes treatment, visit, treatment by visit interaction, age group, baseline DCNVA severity, iris color, and emmetropes/non-emmetropes as factors as well as baseline DCNVA value, and baseline DCNVA value by visit interaction as covariates under the assumption of missing at random (MAR). An unstructured covariance matrix will be used as the covariance structure for

AGN-190584

repeated measurements. A sensitivity analysis will be implemented with the missing data imputed with the average outcome of the vehicle arm under the assumption of missing not at random (MNAR). Change from baseline in photopic, high contrast, binocular DCIVA letters (endpoints 4) will be analyzed with the similar way as change from baseline in mesopic, high contrast, binocular DCNVA letters. Baseline DCIVA will be included as the covariate instead of baseline DCNVA.

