NVPTQ and PICQ scoring algorithms are provided in [Appendix 4](#). Change from baseline in the mesopic NVPTQ Performance score, Mesopic NVPTQ Satisfaction score, PICQ Coping score, and PICQ Impact score (endpoints 4, 9, 10 and 11) will be analyzed using an analysis of covariance (ANCOVA) model that includes treatment, age group, baseline DCNVA severity, iris color, emmetropes/non-emmetropes as factors as well as baseline PRO score as covariate. Also, the cumulative distribution function (CDF) curves will be presented for each of the change from baseline PRO domain scores. The CDF curves (one per domain score for a total of four) represent the cumulative proportion of patients with any particular level of CFB in PRO domain scores at Day 30 Hour 3, by treatment arm. Curves will be produced with a vertical line drawn at the responder threshold.

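### Randomisation is stratified by four factors, but the main test of every responder endpoint ignores them; stratifying the test costs little and recovers modest power if the factors predict response

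*SAP*

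**What the plan says.** SAP 1.1: "This randomization will be stratified by age", and also by baseline binocular DCNVA, iris color and emmetropia. Each factor has two levels, so there are 2 × 2 × 2 × 2 = 16 strata. Protocol 6.3 describes the same scheme and limits two of the factors: "A maximum of 50% (100 per arm) of the participants enrolled will have brown iris color", and non-emmetropes may make up at most 25%.

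For the primary endpoint, SAP 5.3.2 states: "The primary efficacy parameter will be analyzed using a chi-square test with 2-sided 95% confidence interval". The interval uses a pooled-variance normal approximation without continuity correction. Protocol 9.4.1.2 agrees that the endpoint "will be analyzed using chi-square test". SAP 5.4.1 adds: "The key secondary efficacy parameter will be analyzed in the same way as the primary efficacy parameter". SAP 5.4.2 applies the same method to secondary endpoints 1, 3, 6 and 8. The only primary sensitivity analysis, in SAP 5.3.3, is a Wilson-Newcombe interval, which is also unadjusted.

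The continuous endpoints are handled differently. In SAP 5.4.2 the MMRM includes "age group, baseline DCNVA severity, iris color, and emmetropes/non-emmetropes as factors", and the ANCOVA for the patient-reported scores includes "treatment, age group, baseline DCNVA severity, iris color, emmetropes/non-emmetropes as factors as well as baseline PRO score as covariate".

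**The concern.** Stratified randomisation balances the arms on the four factors. If those factors predict response, the difference in proportions varies less from trial to trial than the unstratified chi-square assumes. The test then rejects too rarely under the null hypothesis and has less power than a test that uses the strata. The SAP collects the factors and uses them for the continuous endpoints, but gives no visible reason for leaving them out of the responder endpoints, which include the primary.

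Power matters here because the design has little reserve. The calculation needs 199 per group and the plan has 200. SAP 5.1 then removes all participants at one site from the efficacy analyses, and their number is not given. Under the graphical procedure in SAP 5.4.3, the key secondary endpoint is tested at 0.01.

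**Working it through.** **1. The plan's own figure.** Inputs from SAP 3: p₁ = 0.088, p₂ = 0.184, 200 per group, 2-sided 5%. The mean rate is p̄ = 0.136 and the difference is d = 0.096.

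n = [z₀.₉₇₅ √(2p̄(1−p̄)) + z₀.₈₀ √(p₁(1−p₁) + p₂(1−p₂))]² / d²

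= [1.960 × 0.4848 + 0.8416 × 0.4800]² / 0.009216 = 1.3541² / 0.009216 = 198.96, so 199 per group.

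Power at 200 per group = Φ[(0.096 × √200 − 0.9501) / 0.4800] = Φ(0.849) = 80.2%. The stated 80% or greater is correct for the planned test. At 0.01, Φ[(1.3576 − 1.2487) / 0.4800] = Φ(0.227) = 59.0%.

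**2. The comparison.** In stratum k, let N be the number of participants, n₁ and n₂ the arm sizes, x₂ the active-arm responders and m all responders. The CMH statistic is

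[Σ(x₂ − n₂m/N)]² / Σ[n₁n₂m(N−m) / (N²(N−1))].

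It was compared with the uncorrected chi-square by simulation, with 60,000 replicates per scenario.

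- From the documents: 400 participants, 1:1 allocation, 16 strata, marginal rates of 8.8% and 18.4%, and the caps of 50% brown iris and 25% non-emmetropes.
- Assumed: the odds ratio (OR) of each factor for response, independent factors, 50% in each age and DCNVA group, and permuted blocks of 4 within strata.
- Pooling rule in the CMH: within an age × DCNVA × iris color cell, collapse over emmetropia if either part has fewer than 10 participants.

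Power for the key secondary endpoint, chi-square versus CMH, with iris color and emmetropia at their caps:

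| Assumed factor effect | At 0.05 | Gain (points) | At 0.01 | Gain (points) |
|---|---|---|---|---|
| None | 81.2 vs 81.1% | -0.1 | 59.8 vs 59.6% | -0.2 |
| DCNVA only, OR 2 | 81.2 vs 81.5% | 0.3 | 59.9 vs 60.2% | 0.3 |
| DCNVA only, OR 4 | 81.8 vs 82.9% | 1.1 | 60.3 vs 62.5% | 2.2 |
| All four, moderate (1.5, 2, 1.5, 1.5) | 81.2 vs 81.9% | 0.7 | 59.7 vs 60.8% | 1.1 |
| All four, strong (2, 4, 2, 2) | 82.1 vs 84.2% | 2.1 | 60.1 vs 64.1% | 4.0 |

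ORs are listed in the order age, DCNVA, iris color, emmetropia. Simulated chi-square power with no factor effect is about one point above the formula value, so the gains compare simulated with simulated figures.

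With brown iris at 30% and non-emmetropes at 15%, the gains in the same row order are -0.1, 0.3, 1.2, 0.5 and 1.8 points at 0.05, and -0.2, 0.4, 2.1, 1.0 and 3.8 points at 0.01.

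**3. Type I error.** With a common rate of 8.8% or 13.6% in both arms, chi-square size at nominal 5% is 4.1 to 5.1%, lowest in the strong case. CMH size is 4.9 to 5.2%.

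**4. Other assumed effects.** A separate simulation (100,000 replicates, CMH over all 16 strata without pooling, same prevalences) gave, at 0.05, 81.7 vs 83.1% for OR 2 on each factor, 82.5 vs 85.7% for OR 3 on each, and 83.6 vs 89.4% for OR 5 on each, which is extreme.

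**5. Sparse strata.** At the caps, each of the 8 non-emmetrope cells averages 400 × 0.5 × 0.5 × 0.5 × 0.25 = 12.5 participants, and about 6 to 7 of the 16 cells have no vehicle responder. At 30% and 15%, four cells average 400 × 0.5 × 0.5 × 0.3 × 0.15 = 4.5. The pooling rule collapsed 1.6 of 8 cells on average at the caps and 5.5 of 8 at 30%/15%. Power stayed within 0.2 points of the 16-stratum CMH. Coverage of the 95% interval for the Mantel-Haenszel risk difference (Sato variance) was 94.8 to 95.2%.

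**The case against.** The strongest reply is that nothing is wrong. Protocol and SAP agree on a valid, pre-specified test, and its stated power is met. In every scenario at the caps the chi-square has 81.2 to 82.1% power at 0.05, so power is lost only relative to another test. All of this stands.

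The gain is also small and rests on assumed effects. By the formula, 0.7 points is worth about 3 to 4 participants per group (80.2% at 200, 81.0% at 204). Gains of 2 points or more in the table need an OR of 4 for DCNVA, which no text supports. The one statement bearing on a factor effect is in the summary of changes for Amendment 1. It says the emmetropia effects were dropped from the sample size calculation in light of Study 1883-301-013. That neither shows nor rules out a prognostic effect. These limits stand and keep the point modest.

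The change is not entirely without cost either: it replaces the primary test, alters the estimate and needs a pooling rule. If few non-emmetropes are enrolled, the rule largely removes emmetropia from the stratification. Even so, power and coverage held up after pooling.

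Finally, SAP 5.5 and 5.7.2 cannot be read, so a supportive stratified analysis may exist there. It would not change the main test.

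**Conclusion.** The point holds as an efficiency improvement worth considering; it is not an error. Type I error is protected and the sample size is correct for the chosen test. For the key secondary endpoint, stratifying costs about 0.1 to 0.2 points of power if the factors do not predict response. It gains up to about 2 points at 0.05 and about 4 points at 0.01 under the strong effects in the table. Larger gains need still stronger effects.

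These sizes rest on assumed odds ratios, prevalences, independence of the factors and block size, and on all 400 participants being analysed. The gain for the primary endpoint (the Hour 3 composite) and for the 20/40 endpoints cannot be sized because no rates are given. The low power of the key secondary endpoint at 0.01 comes mainly from the alpha split in SAP 5.4.3, which is a separate matter and is not cured by stratifying.

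**What to change.** Before unmasking, revise SAP 5.3.2 and carry the change to SAP 2, 5.4.1 and 5.4.2, so that it covers the primary and key secondary endpoints and H1, H3, H6 and H8:

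1. Make the main test a CMH test stratified by the four randomisation factors as recorded in IxRS.
2. Report the Mantel-Haenszel common risk difference with a stratified 95% confidence interval.
3. Pre-specify a pooling rule for sparse strata, applied while masked. The rule in the working, with its threshold of 10 participants, is one example.
4. Keep the unstratified chi-square as a supportive analysis.
5. Record the change in SAP Appendix 2, because the chi-square is also protocol text.

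The cost is wording in four SAP sections, one Appendix 2 entry, the pooling rule and a few lines of code. No new data or participants are needed. The reported estimate becomes a stratum-weighted risk difference. If the sponsor prefers to leave the main test alone, a pre-specified supportive stratified analysis is a cheaper alternative, but it would not recover power for the main test.

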### **3. Sample Size Determination**

The primary efficacy parameter is the proportion of participants gaining 3 lines or more from baseline in mesopic, high contrast, binocular DCNVA without losing more than 5-letters of mesopic, high contrast, binocular CDVA with the same refractive correction at Day 30, Hour 3. The key secondary efficacy parameter is the proportion of participants gaining 3 lines or more from baseline in mesopic, high contrast, binocular DCNVA at Day 30, Hour 6. The sample size calculation is based on the key secondary efficacy parameter.

The vehicle group intervention effect and AGN-190584 effect are assumed to be 8.8% and 18.4%, respectively, as observed in the Phase 3 study 1883-301-013. Two hundred (200) participants will be required in each study intervention group to detect the above difference with a power of 80% or greater at the 2-sided 5% significance level.

AGN-190584

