## 5. Statistical Analyses

### 5.1. General Considerations

- Efficacy endpoints will be analyzed using the ITT population, and the safety endpoints will be analyzed using the safety population.
- The baseline for efficacy and safety will be the last non-missing assessment prior to the first administration of study intervention. For participants who were randomized but not treated, the baseline value will be the assessment collected on or prior to the randomization date, whichever is later.
- The change from baseline values will be computed as the postbaseline value minus the baseline value.
- Continuous variables will be summarized by number of participants with observed values (n), mean, standard deviation (SD), median, 1st and 3rd quartiles (Q1, Q3), minimum (min), and maximum (max).
- Categorical variables will be summarized by number of participants with observed values or events (n), frequency count (n1) and percentage of participants with observed values or events.
- All statistical hypothesis tests will be performed at the 2-sided 5% significance level, unless stated otherwise. All confidence intervals will be at least 2-sided 95% confidence intervals.
- In general, statistical analyses will be performed using SAS version 9.4 or higher. MedDRA version 22.1 or higher will be used to code adverse events, biomicroscopy, and medical history. WHODRUG Enhanced B2 will be used to code medications.

To control the overall Type 1 error rate in the efficacy analysis, a gatekeeping testing strategy will be used. All secondary efficacy endpoints will be tested only if the primary efficacy endpoint is statistically significant and the testing procedures are described in the graphical procedure in [Figure 5-1](#).

For primary and key secondary analyses, participants with missing data will be regarded as non-responders. Analyses for other secondary efficacy endpoints will be based on observed data only.

Per confirmation of the site, DCNVA measurements were not conducted correctly for participants at investigator site 051 at screening visit and baseline visit (Day 1 Hour 0). In error, the participants were corrected for near vision rather than distance vision when these

AGN-190584

measurements were taken. Therefore, it is decided to exclude all participants from this site from efficacy analyses. These participants will be included in all safety analyses.

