### **5.3.3. Sensitivity Analysis**

As a sensitivity analysis, a 2-sided 95% confidence interval using Wilson-Newcombe method will be presented.

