**Figure 5-1 Graphical Testing Procedure**

Specifically, 2ry, H2, H3, H4 and H5 will be tested at  $\alpha=0.01$  separately. If 2ry, H2, H3, H4 or H5 is rejected, H7, H8 or H9 will then be tested. If H9 is rejected, H10 and H11 will then be tested. H1 and H6 will be tested only if all other endpoints are significant.

AGN-190584

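### The main 95% interval for responder differences is built on the pooled (null) variance; the excess width is negligible at the documented rates but grows with the effect

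*SAP*

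**What the plan says.** SAP 5.3.2 states that "The primary efficacy parameter will be analyzed using a chi-square test", accompanied by a "2-sided 95% confidence interval based on the normal approximation based on pooled variance without continuity correction". No reason is given for using the pooled variance in the interval. Protocol 9.4.1.2 names only the chi-square test.

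The method reaches six responder endpoints:

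- the primary (1ry), under SAP 5.3.2;
- the key secondary (2ry), which "will be analyzed in the same way as the primary efficacy parameter" (SAP 5.4.1);
- endpoints 1, 3, 6 and 8 (H1, H3, H6, H8), each of which "will be analyzed with the same analysis method as the primary efficacy parameter" (SAP 5.4.2).

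SAP 5.3.3 adds that, as a sensitivity analysis, "a 2-sided 95% confidence interval using Wilson-Newcombe method will be presented". That section stands under the primary endpoint, and the SAP does not say explicitly whether it also applies to the responder secondaries.

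The only response rates given for planning are in SAP 3 (and Protocol 9.2), for the Hour 6 key secondary: "The vehicle group intervention effect and AGN-190584 effect are assumed to be 8.8% and 18.4%, respectively". No rates are given for the primary or for H1, H3, H6 and H8.

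**The concern.** The pooled variance is the variance of the difference when both arms share one response rate. That is the null hypothesis, so it belongs in the test statistic. An interval describes the uncertainty around the difference actually estimated, and once that difference is not zero the pooled variance is the wrong quantity.

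What is at stake is the reported precision of the primary result and of five secondary results. The error depends on the unknown effect, so the plan cannot show that it will be small for the endpoints whose rates it does not give. It also depends on arm balance. SAP 5.1 says of site 051 that "it is decided to exclude all participants from this site from efficacy analyses", and it analyses the other secondary endpoints on observed data only. The analysed arms may therefore depart from 1:1. No test decision is at stake.

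**Working it through.** **Inputs.** Vehicle p1 = 0.088, active p2 = 0.184, d = 0.096, n = 200 per arm, 2-sided 5% (SAP 3). All other rates and arm splits below are assumptions.

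**The plan's own figure.** With p̄ = 0.136, 2p̄(1−p̄) = 0.235008 and p1(1−p1) + p2(1−p2) = 0.080256 + 0.150144 = 0.230400:

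n = [1.96·√0.235008 + 0.8416·√0.2304]² / 0.096² = 199 per arm.

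Power at 200 per arm is 80.2%. The stated 200 per arm for at least 80% power reproduces.

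**Width at the documented rates.**

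- Pooled SE = √(0.235008/200) = 0.03428, half-width 1.96 × SE = 6.72 points, interval 2.88 to 16.32.
- Unpooled SE = √(0.2304/200) = 0.03394, half-width 6.65 points, interval 2.95 to 16.25.
- Ratio = √(0.235008/0.2304) = 1.010.
- For comparison, the Wilson-Newcombe interval is 2.88 to 16.35.

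**Why the excess grows with the effect.** For arms n1 and n2 with N = n1 + n2, algebra gives

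pooled variance = p1(1−p1)/n2 + p2(1−p2)/n1 + d²/N.

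The correct variance is p1(1−p1)/n1 + p2(1−p2)/n2. With equal arms the excess is therefore d²/(2n): here 0.096²/400 = 0.00002304, which equals (0.235008 − 0.2304)/200. With unequal arms the first two terms have their denominators swapped. The excess then also depends on which arm is larger, and it can become negative.

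**Size.** Coverage is from exact binomial enumeration over all pairs of outcomes.

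| Vehicle vs active | Arms (vehicle/active) | Basis | Pooled/unpooled width | Pooled coverage |
|---|---|---|---|---|
| 8.8% vs 18.4% | 200/200 | documented | 1.010 | 95.1% |
| 8.8% vs 18.4% | 192/208 | assumed split | 1.022 | 95.5% |
| 8.8% vs 18.4% | 208/192 | assumed split | 0.998 | 95.0% |
| 10% vs 30% | 200/200 | assumed rates | 1.033 | 95.6% |
| 8.8% vs 30% | 200/200 | assumed rates | 1.038 | 95.7% |
| 40% vs 70% | 200/200 | assumed rates | 1.049 | 96.0% |
| 10% vs 50% | 200/200 | assumed rates | 1.111 | 97.1% |

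**Alternatives at the documented rates, 200/200.** Coverage is 94.8% unpooled, 95.1% Wilson-Newcombe, 95.1% Miettinen-Nurminen, and 94.9% for the score interval without the N/(N−1) factor. At 8.8% vs 30%, 10% vs 30% and 40% vs 70%, Wilson-Newcombe covers 94.9–95.1% and the score interval 94.9–95.0%.

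**Agreement with the test about zero, documented rates.** The pooled interval always agrees with the uncorrected 5% chi-square test, because both use the same statistic at zero. The score interval without N/(N−1) also agrees, for the same reason. Wilson-Newcombe disagrees in 0.29% of trials and Miettinen-Nurminen in 0.28%.

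**The case against.** The strongest case is that this is a preference rather than an error that matters.

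- **No harm at the documented rates.** The planned interval covers 95.1% there, the same as two of the proposed replacements and closer to nominal than the unpooled interval. This stands. The larger effects in the table are assumptions.
- **Coherence.** The pooled interval excludes zero exactly when the uncorrected 5% test rejects, which is a recognised reason to choose it. This stands as an explanation, but the score interval without N/(N−1) gives the same agreement without the wrong variance away from zero. The benefit is also partial: under Figure 5-1, "Specifically, 2ry, H2, H3, H4 and H5 will be tested at" 0.01 each, so for 2ry and H3 a 95% interval does not mirror the initial test whichever method is used.
- **Conservative direction.** With equal arms the interval is too wide and cannot flatter the treatment. That is true, but it misstates precision. The reversal with unequal arms is tiny in the split examined (0.2% of width). Imbalance is also limited: randomisation is 1:1, and missing responses count as failures for the primary and key secondary, so for those two endpoints only the site exclusion can unbalance the denominators.
- **Already covered by Wilson-Newcombe.** It is planned, and the cross-reference in 5.4.1 can reasonably be read to include 5.3.3 for the key secondary. The wording in 5.4.2 is less clear for H1, H3, H6 and H8. In every case the interval remains a sensitivity result, while the pooled interval is the main one.

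**Conclusion.** The concern holds and is minor. The main interval uses a variance that is correct only under the null.

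- At the documented Hour 6 rates with equal arms, the cost is 0.07 points per side (1.0% of width) and coverage is on target.
- The excess becomes visible only with larger differences: roughly 3% to 5% of width at differences of 20 to 30 points for the first three larger-effect pairs in the table, and 11% at 10% vs 50%.
- These larger figures rest on assumed rates, because the documents give none for the primary or for H1, H3, H6 and H8. The unequal-arm figures rest on assumed splits.
- The chi-square p-value, type I error, power and sample size do not change.

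**What to change.** In SAP 5.3.2, name as the main 95% interval either a score interval (Miettinen-Nurminen, or the same interval without the N/(N−1) factor) or the Wilson-Newcombe interval already planned in 5.3.3. Apply it explicitly to 1ry, 2ry, H1, H3, H6 and H8. Keep the pooled variance in the test statistic only, and state that the chi-square test at its allotted alpha governs the conclusion. If agreement with the 5% test about zero is wanted, the score interval without N/(N−1) provides it.

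The cost is one or two sentences and a standard software option. The test, alpha allocation and sample size stay as they are. The one downside, with Wilson-Newcombe or Miettinen-Nurminen, is disagreement with the 5% test about zero in about 0.3% of trials at the documented rates. Stating that the test governs covers this.
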